8.1 Primary study parameter(s)

The primary end point is the MFI-General Fatigue score measured at 12 months after surgery as described earlier. Superiority of the intervention group versus the control group will be assessed using a Mann-Whitney U to test if the two independent samples come from the same distribution.

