1. OBJECTIVES

Primary objective

- To estimate the efficacy of cancer rehabilitation for patients with resectable hepatopancreatobiliary cancer to reduce general fatigue 12 months after discharge as measured by the MFI questionnaire.

Secondary objectives

- To assess the impact of rehabilitation on quality of life (EORTC-QOL C30), Frailty (GFI) and anxiety and depression (HADS).
- To describe the development of MFI-General Fatigue, MFI-Physical Fatigue, MFI-Mental Fatigue, MFI-Reduced Motivation and MFI-Reduced Activity measured preoperatively, at the start and end of the rehabilitation program and six and twelve months after surgery.
- To document the physical status of the patient by measuring the 6 minute walk test, grip and quadriceps strength, muscle mass (L3 muscle index), visceral adipose tissue and malnutrition risk (PG-SGA SF)..
- To describe the general performance of patients using the Karnofsky score, the sit-up and go test and accelerometer activity level measurements.
- To assess patients overall survival at 1, 3, and 5-years after surgery.
- To estimate the cost-utility of the rehabilitation program using QALYs (EQ-5D-5L, QLQ-C30), direct and indirect costs.

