2.4 Sample size calculation

MFI-General fatigue is the primary outcome of the study. To detect a medium difference in MFI-General fatigue (Cohen's $d = 0.50$) with a power of 0.80 and alpha of 0.05 (two sided), both groups should consist of 64 patients. With an expected 20% drop out rate (25), a total of 154 patients are needed.

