8. STATISTICAL ANALYSIS

All data will be collected in an electronically secured safe environment for the participating centres (Open Clinica). Statistical analyses will be performed using SPSS statistical software. Data will be analysed on an intention to treat basis. Adjusted analysis with prognostic baseline characteristics (gender, age, education, marital status, disease stage, radicality of resection) will be performed. This results in increased statistical power, corrects for baseline differences (based on chance) and provides better individualized treatment effect estimates (51). Two-sided p-values <0.05 will be considered significant and clinically important changes will be estimated as effect sizes using Cohen's guidelines. An effect size of 0.2 will be considered as small, 0.5 as medium, and 0.8 as large.

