8.2 Secondary study parameter(s)

Baseline characteristics will be compared between the intervention group and the control group with the independent Student's t-test or the Mann-Whitney test in case of continuous outcome variables and the Chi-square or Fisher's exact test in case of categorical outcome variables where appropriate. A linear mixed model will be used to assess and compare trends in longitudinal fatigue and quality of life data between the two groups, as well as measures of skeletal muscle mass and function, depression and anxiety, frailty, and functional capacity.

Cost-effectiveness analysis

A cost-utility analysis will be performed to identify the most cost-effective treatment (i.e. standard care or rehabilitation program), according to the Dutch guidelines. Both societal and healthcare provider perspectives will be addressed. The time horizon will be 12 months from surgery. The quality of life and costs will be assessed for each study arm. QALYs (based on the EQ-5D-5L) will be the outcome measure for quality of life and costs per QALY for the effectiveness analysis. If no differences in QALYs between the treatment arms are found, a cost-effectiveness analysis will be performed from both societal and healthcare provider perspectives, based on the QLQ-C30. The incremental cost-effectiveness ratios (ICERs), defined as differences in costs of the rehabilitation arm versus the standard care arm divided by the average change in QALYs or HRQoL, of the

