Timed sit-up and go test		x			x		x	x	x
6 Min. walk test					x		x		
Grip strength		x			x		x	x	x
Quadriceps peak force 5 seconds		x			x		x	x	x
8 day accelerometer tracking					x	x	x	x	x
Routine CT used		x			x		x	x	x
MFI questionnaire		x			x		x	x	x
EQ-5D-5L questionnaire		x			x		x	x	x
Life-C30 questionnaire		x			x		x	x	x
iVICQ questionnaire (primary caregiver)		x						x	x
GFI questionnaire		x			x		x	x	x
HADS questionnaire		x			x		x	x	x
PG-SGA SF questionnaire		x			x		x	x	x
Dietary intake assesment				x

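### The deciding test is an unadjusted Mann-Whitney U at 12 months: it cannot carry the adjustment Section 8 promises, leaves the preoperative MFI unused and gives no between-arm difference with a confidence interval

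*Protocol*

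**What the plan says.** - **Objective (Section 1).** "To estimate the efficacy of cancer rehabilitation for patients with resectable hepatopancreatobiliary cancer to reduce general fatigue", measured with the MFI at 12 months. The aim is worded as estimation.
- **Primary test (Section 8.1).** "Superiority of the intervention group versus the control group will be assessed using a Mann-Whitney U to test if the two independent samples" share one distribution. No covariate and no estimator is named.
- **Adjustment (Section 8, opening paragraph).** An adjusted analysis will be done with gender, age, education, marital status, disease stage and radicality of resection. The reason given: "This results in increased statistical power, corrects for baseline differences (based on chance"), with better individualised effect estimates besides. The same paragraph announces effect sizes on Cohen's scale and a two-sided 0.05 threshold.
- **Mixed model (Section 8.2, secondary parameters).** "A linear mixed model will be used to assess and compare trends in longitudinal fatigue and quality of life data".
- **Available data.** Appendix 2 schedules the MFI at screening, two weeks and 17 weeks after discharge, and at 6 and 12 months. Section 6.2 randomises at discharge, stratified by organ and centre, with patients and therapists unblinded.
- **Sample size (Section 2.4).** "To detect a medium difference in MFI-General fatigue" of d = 0.50, "with a power of 0.80 and alpha of 0.05 (two sided), both groups should consist of 64 patients". Then: "With an expected 20% drop out rate (25), a total of 154 patients are needed".

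**The concern.** Section 8 argues that covariate adjustment is worth doing because it raises power and removes chance imbalance. The test that Section 8.1 uses to decide superiority cannot do either. Nor does it produce the quantity that the objective asks for, a between-arm difference with its uncertainty.

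Two further gaps follow. First, the adjusted analysis in Section 8 has no stated rank. If it and the Mann-Whitney fell on opposite sides of 0.05, the protocol would not say what role the adjusted result plays. Second, performing that adjusted analysis as written would not use the baseline value of the outcome, because preoperative MFI-General Fatigue is not on the list. Organ and centre are missing too, although randomisation is stratified on both.

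At stake are some power, a clear decision rule and an interpretable primary result. The validity of the test is not in question.

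**Working it through.** **Inputs.** From Section 2.4: d = 0.50, two-sided alpha 0.05, power 0.80, 64 per group, 20% dropout, 154 in total. From Section 6.2: 1:1 allocation. Assumed, because the protocol gives no value: the correlation r between preoperative and 12-month MFI-General Fatigue, taken from 0.1 to 0.6.

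**Step 1: reproduce the plan's figure.** A two-sample t-test (noncentral t) needs 63.77 per arm, so 64, with power 80.1%. The total follows as 128 x 1.2 = 153.6, so 154. The stated sample size is therefore that of an unadjusted t-test, not of the Mann-Whitney.

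**Step 2: evaluable patients.** 154 x 0.8 = 123.2, or 61.6 per arm.

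**Step 3: power of the named test.** For normal data the Mann-Whitney has efficiency 3/pi = 0.955 relative to the t-test, so its power is that of a t-test on n x 3/pi.
- At 64 per arm: effective n = 61.1, power 78.3% (t-test 80.1%).
- At 61.6 per arm: effective n = 58.8, power 76.7% (t-test 78.6%).

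A simulation on scores rounded and bounded to 4-20 (assumed mean 13, SD 4) gave 77.4% at 64 per arm and 76.9% at 62 per arm for the Mann-Whitney. The rank test itself therefore costs about 2 points.

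**Step 4: power after adjusting for baseline.** Adjustment multiplies the residual SD by sqrt(1 - r²), so the effective effect is 0.5/sqrt(1 - r²). At 61.6 per arm:

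| Assumed r | Effective d | Power | Gain over t-test (78.6%) | Gain over Mann-Whitney (76.7%) |
|---|---|---|---|---|
| 0.1 | 0.503 | 79.0% | 0.4 | 2.3 |
| 0.2 | 0.510 | 80.2% | 1.6 | 3.5 |
| 0.3 | 0.524 | 82.3% | 3.7 | 5.6 |
| 0.4 | 0.546 | 85.2% | 6.6 | 8.5 |
| 0.5 | 0.577 | 88.9% | 10.2 | 12.1 |
| 0.6 | 0.625 | 93.1% | 14.5 | 16.4 |

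Gains are in percentage points. The difference between the last two columns is the 1.9 points from leaving the rank test; the rest is due to baseline.

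**Step 5: which baseline.** The screening MFI precedes randomisation at discharge. The MFI two weeks after discharge follows it in an unblinded trial, so knowledge of allocation could already influence that score. Only the preoperative score is safe as a covariate.

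**The case against.** A Mann-Whitney on randomised arms is a valid test and suits a bounded 4-20 score. Preferring an adjusted model is a matter of efficiency and reporting, and that point stands.

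The power gain also depends on an unknown correlation. The preoperative MFI is taken before major resection and recovery, about a year before the endpoint, and patients are then selected on a fatigue rating of at least 4 at discharge. A weak correlation is plausible. At r = 0.1 to 0.2 the total gain is only 2 to 4 points, about 2 of them from dropping the rank test. This too stands, and is why the range starts at 0.1.

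Some stronger readings are tempting but not supported:

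- A reader might infer that fatigue has three competing analyses with no order. The headings rank two of them: the Mann-Whitney is under the primary parameter, the mixed model under secondary parameters. Only the adjusted analysis in Section 8 is unplaced. It could be run alongside the Mann-Whitney, so this is an unsettled rank rather than a contradiction.
- A reader might infer that the plan contains no effect estimate. Section 8 announces Cohen effect sizes in general terms. What is missing is a link to the primary analysis and a confidence interval.
- A reader might call baseline MFI the strongest available predictor. Nothing in the protocol shows its strength.
- A reader might infer a complete-case primary analysis. Section 8 specifies intention to treat, nowhere specifies complete cases, and missing-data handling may be in an SAP that is not at hand.

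Finally, the shortfall from 64 to 61.6 per arm comes from multiplying by 1.2 instead of dividing by 0.8 (128/0.8 = 160). That is a separate matter and is not charged to the choice of test.

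**Conclusion.** The point holds as a specification weakness with a cheap remedy. The deciding test cannot carry the adjustment that the protocol itself justifies, the rank of that adjustment is unstated, and the covariate list omits preoperative MFI, organ and centre. The primary result as specified would be a p-value, while the objective is an estimate.

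At 61.6 per arm and d = 0.50, power is about 77% with the Mann-Whitney and 79% to 93% after adjusting for preoperative MFI, for r from 0.1 to 0.6. The 80% target is reached from about r = 0.2. These figures assume approximately normal scores, 20% loss spread equally over the arms, and the stated r. They count no gain from the six listed covariates, organ or centre. The documentary findings do not depend on r; only the size of the power gain does.

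**What to change.** In Section 8.1, name one adjusted analysis as primary and say that it alone decides superiority. Either of these would serve:

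- an ANCOVA of 12-month MFI-General Fatigue; or
- the 12-month contrast from the mixed model already planned in Section 8.2, with arm by categorical visit.

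Include preoperative MFI-General Fatigue, organ and centre as covariates, and add them to the list in Section 8. Do not use the MFI taken two weeks after discharge as baseline. Report the 12-month between-arm difference with its 95% CI, and keep the Mann-Whitney as a sensitivity analysis. State in Section 8 how any other adjusted analysis ranks.

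The cost is protocol wording, settled before unblinded outcome data are seen; no new data are needed. There is a small downside: the result then rests on model assumptions for a bounded 4-20 score. If the mixed model is chosen, it assumes data missing at random, so scores missing because of death need a stated interpretation or a sensitivity analysis.

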8.2 Secondary study parameter(s)

Baseline characteristics will be compared between the intervention group and the control group with the independent Student's t-test or the Mann-Whitney test in case of continuous outcome variables and the Chi-square or Fisher's exact test in case of categorical outcome variables where appropriate. A linear mixed model will be used to assess and compare trends in longitudinal fatigue and quality of life data between the two groups, as well as measures of skeletal muscle mass and function, depression and anxiety, frailty, and functional capacity.

Cost-effectiveness analysis

A cost-utility analysis will be performed to identify the most cost-effective treatment (i.e. standard care or rehabilitation program), according to the Dutch guidelines. Both societal and healthcare provider perspectives will be addressed. The time horizon will be 12 months from surgery. The quality of life and costs will be assessed for each study arm. QALYs (based on the EQ-5D-5L) will be the outcome measure for quality of life and costs per QALY for the effectiveness analysis. If no differences in QALYs between the treatment arms are found, a cost-effectiveness analysis will be performed from both societal and healthcare provider perspectives, based on the QLQ-C30. The incremental cost-effectiveness ratios (ICERs), defined as differences in costs of the rehabilitation arm versus the standard care arm divided by the average change in QALYs or HRQoL, of the

arms will be calculated. Sensitivity analyses will be performed to test the sensitivity of various costs per unit of resource. No discounting for costs and effects will be used, due to the relatively short time horizon of 12 months. Direct and indirect costs will be accounted for in the cost analysis and estimated by multiplying resource utilization with the cost per unit of resource following the micro-costing method which is based on comprehensive 'bottom-up' analyses and included costs of employment, material and equipment. In other words, direct costs of each treatment arm will be accounted for. Hospital databases will be used to collect costs. Direct non-medical costs (e.g., travel costs of patients) will be determined using ZIP (postal) codes. The SF-HLW and friction cost approach will be used to take the indirect non-medical costs into account. Sensitivity analyses will be performed for uncertain and variable input variables to perform robust calculations. The cost-effectiveness analysis has been discussed with a healthcare economist.

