6.3 Study procedures

The intervention will be offered close to the patients home. Patients in the control arm are offered standard medical care according to the local protocols.

- ***Dietary Intake***

At discharge all patients will visit a dietary professional to assess their protein and caloric intake.

- ***Physical exercise therapy***

The physical exercise therapy program will start four weeks after hospital discharge for duration of 12 weeks. The intervention group is offered a supervised and personalized exercise program that is aimed at both cardiorespiratory fitness (aerobic training) and muscle strength (resistance training) (48), which is also considered feasible in patients receiving chemotherapy (30). The program is developed in a close collaboration between physiotherapists, exercise physiologists, revalidation specialists, and medical and surgical oncologists. For each patient, an intake or baseline exercise measurement (i.e. 6 minute walk test and muscle function tests) will be performed at their medical center. Subsequently, the program will be specified to each patient's personal preferences and physical fitness with their physiotherapists. Hereafter, patients will train twice a week for one hour under supervision of a physical therapist. Patients are offered the following program: muscle strength training for 30 minutes per session. One training session exists of a minimum of six exercises: 1. Vertical row (longissimus, biceps brachii, and rhomboideus); 2. Leg press (quadriceps, glutei, gastrocnemius); 3. Bench press (pectoralis major, triceps); 4. Pull over (pectoralis, triceps brachii, deltoideus,

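### The economic plan lets the observed QALY result decide whether a QLQ-C30 ICER is produced, with no criterion or order of precedence, and starts its 12-month clock before randomisation

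*Protocol*

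**What the plan says.** Everything here is in the Protocol.

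- **Effect measure.** Section 8.2: "QALYs (based on the EQ-5D-5L) will be the outcome measure for quality of life and costs per QALY for the effectiveness analysis". The next sentence is conditional: "If no differences in QALYs between the treatment arms are found, a cost-effectiveness analysis will be performed from both societal and healthcare provider perspectives". The effect measure in that further analysis is the QLQ-C30. The ICER is then defined with QALYs or HRQoL as alternative denominators. Section 1 lists EQ-5D-5L and QLQ-C30 side by side for the cost-utility objective, with no condition.
- **Horizon.** Section 8.2: "The time horizon will be 12 months from surgery". Sections 6.2 and 9.2 place randomisation at hospital discharge, and Section 6.3 starts the exercise programme four weeks after that.
- **EQ-5D-5L schedule.** Appendix 2 has it at screening, T1 (2 weeks after discharge), T2 (17 weeks), T3 (6 months) and T4 (12 months), all counted from discharge. None is scheduled at discharge itself.
- **Indirect costs.** Section 8.2: "The SF-HLW and friction cost approach will be used to take the indirect non-medical costs into account". Appendix 2 as shown has no row for the SF-HLW.

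**The concern.** A cost-utility analysis should fix its main result before the data are seen. Here a secondary ICER comes into being only if the QALY comparison turns out a certain way, and nothing says which ICER leads when both exist. The trial is sized for a medium effect on fatigue, so failing to find a QALY difference would be weak evidence that there is none.

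The horizon raises a separate problem. Allocation cannot influence anything between surgery and discharge, yet that interval lies inside the 12 months over which costs and QALYs are counted. The same horizon closes before the last utility measurement in Appendix 2.

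Finally, if the SF-HLW really is unscheduled, the productivity data that the plan relies on may not be collected, and they would be hard to recover later. What is at stake is the interpretability of a named secondary objective.

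**Working it through.** **1. Reproducing the plan's own figure.** Section 2.4 uses d=0.50, power 0.80 and two-sided alpha 0.05, giving 64 per group.

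- Normal approximation: n = 2(1.960+0.842)²/0.50² = 62.8, so 63.
- t-test: 63.8, so 64, with power 0.801. The stated 64 is reproduced.

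**2. How often the condition would be met.** The Protocol attaches no rule to the condition. I assume it means p≥0.05, borrowing the general significance level of Section 8. With 20% dropout from 154, the number evaluable is 154×0.8 = 123.2, or 61.6 per arm. The probability of triggering the QLQ-C30 analysis is 1 − power of the two-sample t-test:

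| True QALY effect (d) | About 61.6 per arm | 64 per arm |
|---|---|---|
| 0 | 0.95 | 0.95 |
| 0.2 | 0.80 | 0.80 |
| 0.3 | 0.62 | 0.61 |
| 0.5 | 0.21 | 0.20 |

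As a hand check for d=0.2: 0.2×√(61.6/2) = 1.11, and 1.11−1.96 = −0.85, so power is about 0.20. Under this reading, a small but real QALY gain would usually be labelled as no difference.

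**3. The clock.** Setting the sections side by side:

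- Horizon: day 0 is surgery; it ends 12 months after surgery (Section 8.2).
- Randomisation: at discharge (Sections 6.2 and 9.2).
- Last EQ-5D-5L: 12 months after discharge (Appendix 2, T4).

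The documents give no length of stay. For an assumed stay of 7 to 30 days, 7/365 = 2% to 30/365 = 8% of the horizon precedes randomisation. T4 then falls on day 372 to 395 after surgery, 7 to 30 days after the horizon has closed.

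**4. Effect on the cost difference, if the index admission is costed.** Let k be the SD of index-admission cost divided by the SD of post-discharge cost, with the two components independent. The SE of the between-arm difference is multiplied by √(1+k²). The documents give no cost SDs, so k is assumed:

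- k=0.5: √1.25 = 1.12, up 12%.
- k=1: √2 = 1.41, up 41%.
- k=1.5: √3.25 = 1.80, up 80%.

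Because randomisation follows the admission, the expected difference in this component is zero. It adds variance and chance imbalance, not systematic bias.

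**5. Starting utility.** Moving the clock to discharge leaves no EQ-5D-5L at time zero. The nearest measurements are screening (before surgery) and T1. T1 comes before exercise starts, but after allocation, which patients know.

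**The case against.** The strongest defence is that the fallback is pre-specified and adds to the QALY analysis. The cost-utility analysis is promised without condition, no sentence says that its result is dropped, and the two denominators may simply cover both analyses. That stands against inferring that QLQ-C30 replaces QALYs. It does not answer the missing criterion or the missing order of precedence.

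A reader might also treat the two measures as two chances at significance. With no true effect, the chance that at least one reaches p<0.05 is about 8% to 10% (9.5% at correlation 0.3, 8.4% at 0.7). But an ICER is an estimate, quality of life is analysed as a secondary outcome anyway, and always reporting both measures leaves that figure unchanged. It is no argument for the fix.

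On costs, no sentence says that the index admission is counted; this is inferred from the horizon and the lack of an exclusion. Since k is unknown, calling the cost difference swamped would be unsupported.

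Setting "Hospital databases will be used to collect costs" beside "The intervention will be offered close to the patients home" in Section 6.3, a reader might infer that the societal perspective cannot be computed. The documents do not support that. Section 8.2 also provides bottom-up micro-costing and travel costs from postal codes, the planned volume of sessions is fixed in Section 6.3, and Appendix 2 includes a caregiver questionnaire. The missing SF-HLW row rests on a table read from PDF, so it needs checking.

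On timing, Section 6.1.2 counts the 6- and 12-month assessments from surgery, which agrees with the horizon. The mismatch is with Appendix 2, the only place that schedules the EQ-5D-5L.

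Methods for uncertainty intervals may be in an analysis plan that is not shown, and are not criticised here.

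**Conclusion.** The point holds in a limited form. The production of a QLQ-C30 ICER depends on the observed QALY result, without a criterion, and the Protocol does not say which ICER is the main one. The 80% trigger rate at d=0.2 rests on reading no difference as p≥0.05. The horizon includes time before randomisation and, on Appendix 2's timing, ends before the last EQ-5D-5L; both follow from the text. The 12% to 80% inflation of the SE rests on assumed SD ratios and on the index admission being costed, and it is a loss of precision only. The SF-HLW gap is a discrepancy to reconcile. All of this concerns a secondary economic objective; the primary fatigue comparison is untouched.

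**What to change.** In Section 8.2:

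- Delete the condition. State that the QALY-based ICER is always reported as the main economic result, and the QLQ-C30-based ICER always as a secondary analysis. Align the wording of the objective in Section 1.
- Start the 12-month horizon for costs and QALYs at randomisation (discharge), ending at T4. Index-admission costs then fall outside the comparison.
- Define the starting utility in advance from an available EQ-5D-5L, for example T1, and state how the interval from discharge to that visit is handled.

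In Appendix 2, check the full table. If the SF-HLW is indeed absent, schedule it at the follow-up visits.

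The cost is a few sentences, one explicit assumption about the starting utility and, if needed, one short questionnaire that the Protocol already names. Sample size and the primary analysis do not change.

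### Section 8.2 does not state the ICER denominator as a between-arm difference, and the listed covariates leave out baseline utility

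*Protocol*

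**What the plan says.** Cost-utility is a secondary objective in Section 1: "To estimate the cost-utility of the rehabilitation program using QALYs (EQ-5D-5L, QLQ-C30), direct and indirect costs". Section 8.2 gives the purpose of the analysis as "to identify the most cost-effective treatment (i.e. standard care or rehabilitation program), according to the Dutch guidelines", with a horizon of 12 months from surgery and QALYs derived from the EQ-5D-5L. If the arms do not differ in QALYs, a cost-effectiveness analysis based on the QLQ-C30 follows.

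The result measure is then defined in one sentence. It opens with "The incremental cost-effectiveness ratios (ICERs", which are "defined as differences in costs of the rehabilitation arm versus the standard care arm divided by the average change in QALYs or HRQoL". The part on the denominator runs "divided by the average change in QALYs or HRQoL, of the", and after a page break the sentence ends "arms will be calculated".

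On covariates, the opening of Section 8 plans an adjusted analysis and lists gender, age, education, marital status, disease stage and radicality of resection. Baseline utility is not listed. The schedule in Appendix 2 has the EQ-5D-5L and the QLQ-C30 at screening (T0.1), and Section 6.2 places randomisation at hospital discharge.

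**The concern.** An ICER divides a between-arm difference in mean cost by the between-arm difference in mean effect for the same two arms. Here only the numerator is written that way. *Average change* would ordinarily be taken as change over time. For QALYs that has no clear meaning within an arm, because a QALY total accumulates over the 12 months. For the QLQ-C30 it has an obvious meaning, the mean change from baseline, and that is the wrong quantity for this ratio. Patients in both arms may change over the year after major surgery whatever the programme does. A ratio built on that change stays finite when the programme adds nothing, and it can hide the sign when the programme does harm.

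Baseline utility affects the same denominator. QALYs are computed from utility over the year, so a chance difference in utility before randomisation enters the QALY difference to the extent that it persists, unless it is adjusted for.

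**Working it through.** The protocol gives no cost, QALY or ICER figure, so there is nothing to reproduce. All costs and effects below are assumptions chosen to show how the wording behaves.

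**1. The denominator**

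Let dC be the cost difference, and let a and b be the mean changes under rehabilitation and standard care.

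- Incremental ratio: dC / (a − b)
- One literal reading, averaging the change over both arms: dC / ((a + b)/2)

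With dC = EUR 2,000 (assumed):

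| a | b | a − b | (a + b)/2 | Incremental ratio | Literal ratio |
|---|---|---|---|---|---|
| 0.10 | 0.05 | 0.05 | 0.075 | 40,000 | 26,667 |
| 0.12 | 0.08 | 0.04 | 0.10 | 50,000 | 20,000 |
| 0.08 | 0.03 | 0.05 | 0.055 | 40,000 | 36,364 |
| 0.05 | 0.05 | 0 | 0.05 | undefined | 40,000 |
| 0.03 | 0.05 | −0.02 | 0.04 | −100,000 | 50,000 |

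The distortion is ((a + b)/2) / (a − b). It depends neither on dC nor on the scale of measurement. In the first row it is 0.075 / 0.05 = 1.5; changes of 10 and 5 points on a 0–100 QLQ-C30 scale give 7.5 / 5 = 1.5 as well. In the second row it is 0.10 / 0.04 = 2.5, and in the third 0.055 / 0.05 = 1.1. The last two rows matter most: the literal ratio looks ordinary when there is no benefit and when rehabilitation is worse.

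**2. Baseline utility**

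Inputs: 154 patients in total (Section 2.4), so 154 / 2 = 77 per arm; SD of baseline utility 0.20 (assumed).

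- 95% limit of the chance difference between arms: 1.96 × SD × √(2/77)
- SD 0.20: 1.96 × 0.20 × 0.1612 = 0.063
- SD 0.15: 0.047
- SD 0.25: 0.079

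If half to all of a 0.063 imbalance persists for a year, the QALY difference shifts by 0.063 × 0.5 = 0.03 to 0.063 × 1 = 0.06. Against an assumed true gain of 0.05 and the same EUR 2,000, a shift of 0.03 either way moves the ratio from 40,000 to 2,000 / 0.08 = 25,000 or 2,000 / 0.02 = 100,000. Full persistence against rehabilitation would turn the denominator negative (0.05 − 0.063 = −0.013).

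**The case against.** A reader might infer that the protocol prescribes division by the average over the two arms, and is therefore plainly wrong. The text does not establish that. The words about the arms come after the comma that closes the definition, and they attach most naturally to the ICERs. The ratio is called incremental, the aim is to choose between two arms, and the rule for moving to the QLQ-C30 turns on whether QALYs differ between arms. The analysis is to follow national guidelines and was discussed with a health economist. *Average change* can mean the mean incremental QALYs, and because a within-arm change in QALYs has no clear meaning, that is the sensible reading for QALYs. All of this stands, and it limits the point to wording.

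A reader might go further and divide by the arms' mean QALY totals, which makes the error look enormous. That does not follow the sentence either, since it speaks of change and not of totals.

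The QLQ-C30 rule also gives some protection, because the between-arm QALY difference is examined first. The protection is partial: the fallback uses the same definition with HRQoL in the denominator, which is where change from baseline is most easily read in. The distortion can also be small, as the 1.1-fold row shows.

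On baseline utility, the covariates of an economic model are often left to a separate analysis plan, and one may exist. The omission alone would therefore not be a fault. What remains is that Section 8 does fix a covariate list, and that list lacks the one baseline measure from which the QALY itself is computed. The 0.063 is a 95% limit under an assumed SD, and its persistence through major surgery is also assumed.

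**Conclusion.** The ICER definition in Section 8.2 is badly worded: the denominator is not stated as a between-arm difference, and taken literally as change over time it is not an incremental ratio. In the assumed cases where rehabilitation is better, the literal ratio is too low by 1.1-fold to 2.5-fold (1.5-fold for changes of 0.10 and 0.05). It is positive when the arms do not differ or when rehabilitation is worse. A between-arm difference was probably intended, and under that reading no result would change.

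The baseline point is a worthwhile addition to the same sentence. A chance imbalance of up to about 0.063 in utility (assumed SD 0.20, 77 per arm) could move the QALY difference by an amount comparable with the assumed 0.05 gain, depending on how long it persists.

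Both parts concern a secondary economic analysis. The primary endpoint and the sample size are unaffected.

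**What to change.** Replace the definition in Section 8.2 with: *ICER = difference in mean costs (rehabilitation minus standard care) divided by difference in mean QALYs (rehabilitation minus standard care), with the QALY difference adjusted for EQ-5D-5L utility at screening (T0.1).* State that the QLQ-C30 analysis uses the same between-arm difference, adjusted for the QLQ-C30 score at T0.1.

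Use T0.1 as the baseline for this adjustment, because the next EQ-5D-5L in Appendix 2 (T1, two weeks after discharge) falls after randomisation.

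The cost is one or two sentences. Both questionnaires are already scheduled at T0.1, so no new data, visits or patients are needed.
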